## 5 - Measured variables retained for the analysis

**Table of variables**

| Variables             | Format  | Description                      |
|-----------------------|---------|----------------------------------|
| Code                  | String  | Three letter code of participant |
| Date                  | Date    | Date of data collection          |
| Time                  | Numeric | Time of data collection          |
| Sex                   | Numeric | Sex: male or female              |
| Age                   | Numeric | Age in years                     |
| Marital               | Numeric | Marital status                   |
| Education             | Numeric | Education level                  |
| Self-Health           | Numeric | Self-perceived health            |
| Wt                    | Numeric | Self-reported weight in kg       |
| Ht                    | Numeric | Self-reported height in cm       |
| Order                 | Numeric | Random order of trial            |
| Visit                 | Numeric |                                  |
| Treatment_Drink       | Numeric |                                  |
| Treatment_Recognition | Numeric |                                  |
| Session               | Numeric |                                  |
| BMI_Measured          | Numeric |                                  |
| HR_rest               | Numeric |                                  |
| HR_Peak               | Numeric |                                  |
| RPE_rest              | Numeric |                                  |

|           |         |  |
|-----------|---------|--|
| RPE_Peak  | Numeric |  |
| VO2 rest  | Numeric |  |
| VO2 Peak  | Numeric |  |
| RQ rest   | Numeric |  |
| RQ Peak   | Numeric |  |
| Cytokine1 | Numeric |  |
| Cytokine2 | Numeric |  |
| Cytokine3 | Numeric |  |
| CK        | Numeric |  |

## 6- Statistical Analysis

The statistical analysis will be done according to the intention-to-describe principle. We will report summary statistics according to the type and normality of data. Data will be reported as mean and standard deviation, median and interquartile range for continuous variables and for categorical variables as frequency and percentage. When appropriate data will be reported with a 95 % confidence interval.

### 6.2 Methods of Analysis

#### 6.2.1 Principal Analysis

The Chi-square test will be used to assess the impact of demographics on dependent variables. The repeated measures ANOVA will be used to assess main effects. One way ANOVA and t-test will be used to compare effects of independent variables on measured variables. A p value  $<0.05$  will be considered statistically significant. Effect size will be calculated and presented to provide an estimation of the significance magnitude. If appropriate the 95% confidence interval will be reported.

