### 4.1 Inclusion criteria

The inclusion criteria for this study are the following:

- (1) Recreational athlete, active 5 days a week.
- (2) Male, healthy, non-obese.
- (3) Age 18 to 39 years old.
- (4) No allergies to milk.
- (4) provide consent to participate and able and ready to complete the study's interview.
- (5) Speaking and understanding Arabic or English, and open to visit him at home.
- (6) Subject consenting to participate in the study.

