#### 4.4 Sample size calculation

Sample size was calculated with the use of G\*Power 3. 1.9.7 that revealed the need for 12 participants to achieve a 0.95 power of the test with medium effect size and alpha set at a 0.05 value. Thus, a minimum of 12 participants will be recruited for the current study.

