#### 6.2.2 Secondary Analysis

The same methods will be used to assess the impact inflammation markers.

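### The SAP assigns chi-square to demographics against continuous outcomes in about 12 men with no categorisation planned, and Table 8.1 gives a p value for age across visits of the same men

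*SAP*

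**What the plan says.** SAP section 6.2.1 (Principal Analysis) opens: "The Chi-square test will be used to assess the impact of demographics on dependent variables". It then gives main effects to repeated measures ANOVA and adds: "One way ANOVA and t-test will be used to compare effects of independent variables on measured variables". A p value below 0.05 "will be considered statistically significant". Section 6.2.2 adds: "The same methods will be used to assess the impact inflammation markers".

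The variable table in SAP section 5 lists resting and peak heart rate, RPE, VO2 and RQ, three cytokines and CK. The protocol expresses VO2 max in mL/kg/min and IL-6 in pg/mL. Neither document gives a cut-point or a rule for grouping any outcome.

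Section 4 describes a randomised crossover, so the same men return. On numbers, section 4.4 says "a minimum of 12 participants will be recruited for the current study". Eligibility under section 4.1 is "Male, healthy, non-obese", while the variable table describes one demographic as "Sex: male or female".

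Table 8.1, the shell for demographic characteristics, has columns for visits 1, 2 and 3, a missing count and a p value. Its rows are age, self-rated health and resting heart rate. No test is named for the p value.

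**The concern.** A chi-square test compares counts in categories. The outcomes that matter here are measurements, so the sentence can be carried out only by treating each distinct value as a category or by cutting the outcome at a point chosen later. The first gives an answer that does not depend on the data. The second leaves the cut-point open after the data are seen and rests on a large-sample approximation that 12 men cannot support.

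Table 8.1 raises a related problem. Its visit columns hold the same men, so they are not independent groups, and a man's age does not respond to anything in the trial.

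At stake are p values that would be read against 0.05 under the heading of the principal analysis, and again for the inflammatory markers, without a sound interpretation. They also do not serve the objective: in a crossover each man is his own control, so a fixed characteristic cannot confound the within-man drink comparison.

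**Working it through.** **Inputs.** n = 12 (SAP 4.4, a minimum); alpha = 0.05 (6.2.1); three visits per man (assumed from the columns of Table 8.1); within-man correlation 0.5 to 0.9 (assumed, not in the documents).

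**The plan's own figure.** Section 4.4 derives 12 from "0.95 power of the test with medium effect size and alpha set at a 0.05 value". This can be neither reproduced nor refuted, because the test, the number of measurements and their correlation are not stated. Taking medium as f = 0.25 in a repeated measures ANOVA, three measurements at correlation 0.5 need 43 men, while six at correlation 0.8 need 12. The figure is used below only as the number of men.

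**1. Raw values, one per man.** If all n outcomes are distinct and there are k demographic groups, the Pearson statistic is always n(k − 1) on (n − 1)(k − 1) degrees of freedom.
- k = 2: 12 on 11 df, p = 0.364.
- k = 3: 24 on 22 df, p = 0.347.

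Neither value can change with the data.

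**2. Median split, one row per man.** The mean expected count in an r × c table is 12/(rc): 3.0 for 2×2, 2.0 for 2×3 and 1.3 for 3×3. The smallest is therefore at most 3 in any table, and at least one cell is below 5. The exact size of the 2×2 test comes from the hypergeometric distribution with C(12,6) = 924 equally likely allocations. Counting those with a statistic above 3.84:

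| Demographic split | Uncorrected | Yates-corrected |
|---|---|---|
| 6/6 | 74/924 = 0.080 | 2/924 = 0.002 |
| 5/7 | 14/924 = 0.015 | 14/924 = 0.015 |
| 4/8 | 56/924 = 0.061 | 0 |
| 3/9 | 168/924 = 0.182 | 0 |
| 2/10 or 1/11 | 0 | 0 |

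The size depends on how the 12 men happen to divide, not on the nominal 0.05.

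**3. Visit rows pooled as if independent (12 × 3 = 36 rows).** Simulated size, uncorrected, with the outcome cut at the median:
- demographic split fixed at 6/6: 0.20, 0.24 and 0.32 at correlations 0.5, 0.7 and 0.9;
- random binary demographic: about 0.15 at 0.5, 0.21 at 0.8 and 0.25 at 0.9.

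Part of the 6/6 excess is discreteness. With 36 truly independent rows in an 18/18 by 18/18 table, the test rejects when one group has at least 12 or at most 6 high values, which has exact probability 0.094. With continuity correction, the pooled size over correlations 0.5 to 0.9 is about 0.07 to 0.16.

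**4. Table 8.1.**
- Age, with the same values at three visits: one-way ANOVA gives F = 0, p = 1.00; the Friedman test is undefined; if one man has a birthday, p = 0.999.
- Resting heart rate: a one-way ANOVA across visits that ignores pairing has simulated size 0.0065, 0.0009 and 0.000 at correlations 0.5, 0.7 and 0.9, so it would almost never detect a change. A paired or repeated-measures test would be usable.
- Self-rated health: a chi-square across visits would treat each man's three answers as coming from three different men.

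**The case against.** The strongest reply is that the sentence does little harm. Repeated measures ANOVA is the method given for main effects, and the SAP also names ANOVA and t-tests, which suit continuous outcomes. This stands as far as the drink comparison goes. A reader might infer that the principal result is compromised because chi-square is mentioned first; sentence order is not rank, and the documents do not support that.

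Several other stronger readings also fail.

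- **Every p value in Table 8.1 is invalid.** No test is named there, and self-rated health and resting heart rate can change between visits, so a paired test on those rows would be valid. Only the age row has nothing to test, and with p at or near 1 it cannot produce a false positive.
- **The plan has a type I error near 21%.** That figure needs visit rows pooled as independent, an uncorrected test and an assumed correlation of 0.8. The SAP states none of these.
- **Every expected count is below 5.** At least one is. With a 10/2 split on both margins, one cell expects 10 × 10/12 = 8.3. Twelve is also a floor, so more men may be enrolled.
- **The variable table proves the outcomes continuous.** Its format column is a storage type; marital status and education are numeric there too. The conclusion rests on what the variables are and on the protocol's units. Treatment_Recognition may well be categorical.
- **Each visit mixes all drinks, so the table hides the drink contrast.** The documents state neither the number of drinks nor the purpose of each visit, and the shell is headed as demographic.
- **Sex will be tested.** It is listed with two levels although only men are eligible, but no section says it will be tested. It would be constant if it were.

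**Conclusion.** The point holds in a limited form. As written, section 6.2.1 assigns chi-square to outcomes it does not fit, section 6.2.2 extends this to the inflammatory markers, and no categorisation makes it workable. With 12 men the result is either a fixed p (0.364 or 0.347) or, after a median split, an uncorrected test whose size lies anywhere from 0 to 0.18. These figures need no assumption beyond n = 12, distinct values in the first case and a 2×2 table in the second. The range 0.15 to 0.32 is conditional on pooling three visits per man without correction, at assumed correlations of 0.5 to 0.9.

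In Table 8.1 the p value is meaningless for age and sound for the other two rows only with a paired method. The drink comparison by repeated measures ANOVA stands apart from all of this, so this is a correction the SAP should make, not a threat to its main result.

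**What to change.** - In section 6.2.1, remove chi-square for the continuous outcomes and for RPE. Keep an exact test only for items that are truly categorical, such as Treatment_Recognition if it is recorded that way. Section 6.2.2 then follows.
- If a demographic effect is wanted, use one value per man: for example, regress his within-man drink difference on age, or enter age as a covariate in the repeated-measures model already planned. Label it exploratory.
- Describe demographics once per man, without a p value.
- For any row compared across visits, such as self-rated health or resting heart rate, name a paired or repeated-measures method.

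The cost is a few sentences of SAP wording and one table shell. Data collection and sample size do not change.

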## 4 - Project Design

The study will use randomized crossover counterbalanced design to collect information about impact of camel milk on physical performance.

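### The SAP's principal analysis lists paired and possibly unpaired methods without saying which decides the drink comparison, and names no period term

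*SAP*

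**What the plan says.** SAP section 4 sets the design: "The study will use randomized crossover counterbalanced design". Neither document gives the number of drinks, the sequences or a washout.

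SAP section 6.2.1 assigns chi-square to demographics and then names two sets of methods in consecutive sentences:

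- "The repeated measures ANOVA will be used to assess main effects". The within-subject factors are not named.
- "One way ANOVA and t-test will be used to compare effects of independent variables on measured variables". The independent variables are not listed, and the t-test is not described as paired or independent.

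Section 6.2.2 carries the whole set over to the secondary outcomes: "The same methods will be used to assess the impact inflammation markers".

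The variable table in section 5 includes Treatment_Drink, Visit, Session and Order. Order is described as "Random order of trial"; the other three have no description. Visit appears again only as column headings 1 to 3 in the descriptive table of section 8.1. None of the four is named as a factor in any analysis.

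**The concern.** In a crossover each man is measured under every drink, and the design is efficient because drinks are compared within the same man. One-way ANOVA and the independent t-test treat the values under each drink as coming from different men, so variation between men stays in the error term. Repeated measures ANOVA removes it.

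Section 6.2.1 lists both kinds of method and ranks neither. An analyst could follow it with a test that uses the pairing or with one that does not, and with 12 men the two can give very different answers on the same data.

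The second gap is period. Fitness, familiarity with the test or residual soreness may shift results from one visit to the next. If the model has no period term, any such shift becomes residual error.

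Both gaps extend to the inflammatory markers through section 6.2.2.

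**Working it through.** **Plan's own figure.** Section 4.4 gives 12 participants for 0.95 power, a medium effect and alpha 0.05. It states no test family, numerical effect size, number of measurements or correlation, so the figure can be neither confirmed nor refuted from the documents. Only N = 12 and alpha = 0.05 are used here. Whether 12 is enough is a separate question.

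**Assumptions not in the documents.** Two drinks; total SD of 1 under each drink; drink difference d = 0.5 SD; correlation rho between a man's values of 0.5 or 0.8; two-sided tests; complete data; six men in each order where period is considered.

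**Step 1: standard error of the drink difference.**

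- Pairing used: SE = sqrt(2(1 - rho)/12), which is 0.289 at rho = 0.5 and 0.183 at rho = 0.8.
- Pairing ignored: SE = sqrt(2/12) = 0.408 at any rho.
- Ratio = 1/sqrt(1 - rho): 0.408/0.289 = 1.41 and 0.408/0.183 = 2.24.

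**Step 2: power and type I error.** The paired analysis has noncentrality 0.5/SE on 11 degrees of freedom: 0.5/0.289 = 1.73 (power 0.35) and 0.5/0.183 = 2.74 (power 0.70). The unpaired figures come from simulation.

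| rho | SE ratio | Power, unpaired | Power, paired | Type I error, unpaired |
|---|---|---|---|---|
| 0.5 | 1.41 | 0.15 | 0.35 | 0.009 |
| 0.8 | 2.24 | 0.08 to 0.09 | 0.70 | below 0.001 |

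The paired test keeps its nominal 0.05. For two drinks, one-way ANOVA is the same test as the independent t-test. Simulated with three drinks at rho = 0.8 (effect size f = 0.25), power is 0.06 for one-way ANOVA and 0.80 for repeated measures ANOVA, so the pattern is the same.

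**Step 3: leaving out period.** Let the within-person SD be 1, the true drink effect 1 and the assumed period shift 1, with six men in each order. Each man's drink difference has variance 2 from measurement. The shift adds +1 to the differences in one order and -1 in the other. The mean over the two balanced orders is unchanged, so the drink estimate is unbiased, but without a period term the spread of plus or minus 1 is counted as error.

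| Analysis | Power | Type I error |
|---|---|---|
| Paired, no period term | 0.42 | 0.018 |
| Paired, period term | 0.60 | 0.05 |

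If there is no shift, the term costs almost nothing. In the setting of Step 2, simulated power without and with it is 0.36 and 0.35 at rho = 0.5, and 0.70 and 0.69 at rho = 0.8.

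**Step 4: Order.** Randomised order is a between-man factor. In complete, balanced data the participant effect already absorbs it, so adding Order does not change the standard error of the within-man drink contrast. Only the period term can.

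**The case against.** A reader might infer that the SAP ignores the pairing of the crossover and that its standard errors are therefore wrong. The documents do not support that:

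- **A paired method is listed.** Repeated measures ANOVA for main effects uses the within-man pairing. If it decides the drink comparison, the loss in Steps 1 and 2 does not arise.
- **Drink is not named in the disputed sentence.** It refers only to independent variables. Section 5 retains between-man characteristics such as marital status, education and self-perceived health. With one row per man, a one-way ANOVA or independent t-test on these would not be a pairing error.
- **The t-test may be paired.** The SAP does not say that it is independent.
- **The missing Order term is harmless to the drink standard error** in complete, balanced data (Step 4).
- **The period loss rests on an assumed shift.** With none, a period term loses about 0.01 of power.
- **The errors are conservative for drink** when rho is positive, and balanced sequences protect the estimate from period bias.

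All of these stand, and they limit the point to an ambiguity with a conditional cost. They do not remove it. Demographics have already been assigned to chi-square, and Treatment_Drink is the experimental factor, so applying the sentence to drink is a natural reading. Nothing in section 6.2.1 says that repeated measures ANOVA takes precedence or which factors it contains. Protection from period bias also depends on balance, which dropout could disturb.

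**Conclusion.** The point holds as an unresolved choice of method plus an omitted period term. Section 6.2.1 does not identify the deciding drink analysis, leaves the t-test unspecified, and models no period effect.

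The cost is conditional. If an unpaired method is applied to drink, the standard error is 1.41 times too large at rho = 0.5 and 2.24 times at rho = 0.8, and more than half the power is lost at either value in the two-drink case with d = 0.5. If a paired method is used without period, the drink estimate stays unbiased under balanced sequences, and power falls only to the extent that a shift exists. Neither gap raises the false-positive rate for drink. The danger is a missed effect.

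The correlation, the number of drinks, the effect size and the period shift are all assumptions, so the figures show scale and do not predict this trial's results. The wording should still be settled before the data are analysed, because with 12 men the choice of test can decide the result.

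**What to change.** In section 6.2.1, name one primary within-participant model for the drink effect, and apply it to the inflammatory markers through section 6.2.2:

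- Use a linear mixed model with a random participant effect (Code), or an equivalent repeated measures analysis with its factors stated.
- Include fixed effects for Treatment_Drink and period. Section 5 should first define Visit as the treatment period and say whether any visit is a baseline without a drink.
- Define Session, and add it to the model if outcomes are repeated within a visit.
- Order may be added as the sequence term, but the drink standard error does not need it.
- Take the drink contrasts and their 95% confidence intervals from this model.
- State that any t-test on drink is paired, and remove one-way ANOVA for drink comparisons.
- If the one-way ANOVA and t-test sentence is meant for between-man characteristics, list them and specify one row per man.

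The cost is SAP wording, SPSS syntax and a few degrees of freedom. The variables are already collected.

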#### 6.2.2 Secondary Analysis

The same methods will be used to assess the impact inflammation markers.

### 6.3 Specific methods for handling missing data

The researchers will perform a missing data analysis to report on the mode and the percentage of missing values. Variables with less than 5% of missing values will be imputed with the use of median for the continuous variables and/or the highest frequency for the categorical variables. In the case of missing values higher than 5%, the variable will be excluded from the final analysis.

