#### **- The guidelines for the assessment of the maximal oxygen consumption ( $VO_{2\text{ MAX}}$ ) **

1. Place the necessary sensors and electrodes on the participant, which may include a face and a pulse oximeter for monitoring oxygen saturation prior to the start of the training.
2. Calibrate the metabolic cart to room temperature (21 – 23 °C) and to gases of the concentration (16.00%  $O_2$  and 3.99%  $CO_2$ )
3.  $VO_2$  is recorded every 15 seconds during the exercise as, and when it reaches a plateau, the  $VO_{2\text{ MAX}}$  is achieved.
4.  $VO_{2\text{ MAX}}$  is expressed in mL of oxygen / kg of body weight (mL/Kg/min).

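### The SAP's 5% missing-data rule exempts no outcome and defines no denominator, so with 12 men one dropout can remove the primary outcomes; below 5%, median filling ignores the within-man pairing

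*SAP*

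**What the plan says.** SAP 6.3 holds the plan's only method for missing data. It has two branches, applied variable by variable.

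- Low missingness: "Variables with less than 5% of missing values will be imputed with the use of median for the continuous variables". It does not say whether the median is taken over all values, by drink or by visit.
- High missingness: "In the case of missing values higher than 5%, the variable will be excluded from the final analysis". No outcome is exempt, and the denominator of the percentage is not defined.

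SAP 4.4 states that "a minimum of 12 participants will be recruited for the current study". That is the calculated need itself, with no allowance for dropout. SAP 4 describes the design: "The study will use randomized crossover counterbalanced design". SAP 6.2.1 names repeated measures ANOVA for main effects, and SAP 6.2.2 carries the same methods over to the inflammatory markers. The SAP 5 variable table lists Visit, Treatment_Drink and Session as variables, and the SAP 8.1 table shell shows visits 1 to 3.

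**The concern.** A percentage threshold that would be mild in a large survey is severe with 12 people. One man is more than 5% of the sample, so one dropout can move an outcome from analysed to discarded, and 11 men's complete crossover data go with it. The outcomes that serve the primary objective (SAP 3.1) have no protection.

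Because the denominator is undefined, the same gap can lead to imputation or to exclusion. Whether the main question is analysed could then be settled after the data are seen.

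The imputation branch has a separate weakness. A crossover gains its precision from comparing each man with himself. A group median carries no information about the man whose value is missing, yet it enters the analysis as if it had been observed.

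**Working it through.** **Inputs.** N = 12 (SAP 4.4, a minimum); threshold 5% (SAP 6.3); three visits (SAP 8.1 shell). The documents do not give the number of drinks or sessions, a dropout rate or a within-man correlation, so those below are assumptions. The N of 12 cannot be reproduced, because SAP 4.4 does not state the test family, number of measurements or correlation. This point needs only the N itself.

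**1. When the rule excludes a variable.** Share missing = missing values / total values.

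| Denominator | Gap | Share | Result |
|---|---|---|---|
| Per condition, 12 values | one man, one condition | 1/12 = 8.3% | excluded |
| All rows, 12 × 3 = 36 | one missed visit | 1/36 = 2.8% | imputed |
| All rows, 36 | one man leaves after visit 1 | 2/36 = 5.6% | excluded |
| All rows, 12 × 2 = 24 | one missed visit | 1/24 = 4.2% | imputed |
| All rows, 24 | two missing values | 2/24 = 8.3% | excluded |

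If all sessions of a visit are lost together, the number of sessions cancels and these shares do not change. Counted per condition at N = 12, the smallest non-zero share is 8.3%, so the imputation branch can never apply. One man exceeds 5% per condition up to N = 19 (1/19 = 5.3%) and falls below it only from N = 21 (1/21 = 4.8%).

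**2. How often a variable would be dropped.** P(dropped) = 1 − P(X ≤ k), where X is binomial (rows, q), q is an assumed independent per-value missing rate, and k is the largest count below 5%.

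| Values | k | q = 2% | q = 5% |
|---|---|---|---|
| 12 | 0 | 22% | 46% |
| 24 | 1 | 8% | 34% |
| 36 | 1 | 16% | 54% |

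For 12 values at 5% this is 1 − 0.95^12 = 0.46. The same expression gives the chance that at least one of 12 men drops out: 0.46, 0.72 and 0.93 at assumed dropout of 5%, 10% and 20%.

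**3. What median filling does.** Assumptions: 12 men, two drinks, one of 24 values missing completely at random, each value with SD 1, true difference 0.5 SD, paired t-test at two-sided 0.05. For the 11 observed pairs, the SD of differences is √(2(1 − ρ)) and the noncentrality is √11 × 0.5/√(2(1 − ρ)). This is 1.66, 2.62 and 3.71 at ρ = 0.5, 0.8 and 0.9, on 10 degrees of freedom. The filled cases come from simulation.

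| ρ | 11 observed pairs | Pooled median | Drink-specific median |
|---|---|---|---|
| 0.5 | 0.32 | 0.33 | 0.36 |
| 0.8 | 0.66 | 0.61 | 0.65 |
| 0.9 | 0.92 | 0.82 | 0.85 |

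With the pooled median the mean difference shrinks from 0.50 to 0.48. The average SD of differences rises from 0.618 to 0.659 at ρ = 0.8 (+7%) and from 0.437 to 0.505 at ρ = 0.9 (+16%). A drink-specific median removes the shrinkage but still loses power at 0.9. In separate runs with no true difference, Type I error stayed between 0.046 and 0.058, so the harm is mainly to precision.

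**The case against.** The best defence is that exclusion is not automatic. The SAP 5 variable table suggests a long file with one row per man, visit and session. In such a file one missed visit is 2.8% of 36 rows, or 4.2% of 24, and is imputed. Twelve is also a minimum: with 14 men and three visits, a man who leaves after visit 1 gives 2/42 = 4.8% and no longer triggers exclusion. All of this stands, and it rules out the inference that a single missed visit always deletes the primary outcomes. It does not rescue the rule. SAP 6.3 fixes no denominator, a repeated measures ANOVA is commonly run with one column per condition, and at the planned 12 men a dropout after the first of three visits crosses the threshold even in the long file.

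A second defence is that imputation does little harm. That is true at correlation 0.5, so a reader should not infer that filling is always worse than using the observed pairs. The loss appears at high correlation, and pooling the median is only one reading of SAP 6.3.

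Three further inferences are not supported:

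- **No VO2 plateau means a missing value.** The protocol's VO2 max guideline says the maximum is achieved "when it reaches a plateau", but SAP 5 lists VO2 Peak, which exists without a plateau. Nothing tells staff to blank it.
- **Cytokine results below detection trigger the rule.** Neither document mentions non-detects or how they are coded.
- **Exactly 5% falls between the branches.** The wording does leave that gap, but 5% of 12, 24 or 36 values is 0.6, 1.2 or 1.8, so it cannot occur at those counts.

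**Conclusion.** The exclusion rule is wrong as written and should be corrected before the data are analysed. Followed literally with 12 men, it can discard every affected outcome, primary ones included, because of one dropout. This happens if the percentage is taken per condition (8.3%), or over 36 rows when a man leaves after the first of three visits (5.6%). It does not happen for one missed visit in a long file. Under assumed independent missing rates of 2% to 5%, the chance that a given variable is dropped runs from 8% to 54%, depending on the rate and the denominator. The binomial treats gaps as independent, whereas a dropout loses several values together, so these figures indicate scale and are not forecasts.

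The imputation branch is a lesser fault. It discards the pairing in principle. Its cost in power ranges from nothing at correlation 0.5 to about 0.10 at 0.9 with a pooled median, under the assumed difference of 0.5 SD. The documents give no correlation, so where the trial lies in that range is unknown.

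**What to change.** For outcome variables, delete both the 5% exclusion and the median imputation from SAP 6.3. In their place, specify:

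- a linear mixed model for each outcome, fitted to all observed values with SPSS MIXED (SPSS 29 is already the named software);
- participant as a random effect; drink and visit (period) as fixed effects; and, where an outcome is measured repeatedly within a visit, session and drink-by-session as further fixed effects;
- REML estimation with Kenward-Roger or Satterthwaite degrees of freedom, which matters with about 12 men;
- the number of observed values per drink, reported for each outcome;
- a complete-pairs analysis as a sensitivity check.

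The cost is a change of SAP wording, with no new data or visits. There are two small downsides. It is a modest departure from the planned repeated measures ANOVA, and the model is valid if values are missing at random, an assumption the SAP should state.
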